5.3.6.3 Device Related Re-intervention

Device related re-intervention will be summarized by scheduled visits for re-intervention reasons, related to AE, time to re-intervention from operation, failed anchors, whether or not the component well fixed was in place, the component damage, the component removed or revised, and component description. A listing of device-related re-intervention will be provided.

5.3.6.4 Device Deficiencies (DDs)

DDs will be summarized by scheduled visits for deficiency category, related to AE, investigational product reference number, timing of deficiency, time to deficiency from operation if post operation, and if product returned to sponsor. A listing of DDs will be provided.

5.3.6.5 Concomitant Medication/Therapy

Medications/therapies will be classified as Concomitant if used in the period from operation date to the 12-month visit. Concomitant medications until end of study will be summarized by generic name and indication. A by-subject listing of concomitant medications will be provided.

5.4 Study Subjects

5.4.1 Disposition of Subjects

Disposition information will be tabulated and summarized with descriptive statistics. This summary includes, but, is not limited to: total enrolled, total completed 6-month visit, total completed 12-month visit, total completed or terminated early in the study and reasons for discontinuation. End of study status will be listed.

5.4.2 Protocol Deviations

Major protocol deviations are defined as those deviations from the protocol that are likely to have an impact on subject's right, safety, well-being, and/or the validity of data for analysis. Major protocol deviations and any action to be taken regarding the exclusion of subjects or affected data from specific analyses are defined in the project-specific Protocol Deviation Specification.

Subjects with major protocol deviations will be listed. Protocol deviations will be based on clinical review mainly of the following categories: (1) Entered but did not satisfy eligibility criteria; (2) other.

A summary of the number and percentage of enrolled subjects with a major protocol deviation by category of deviation will be provided.

5.5 Demographic and Other Baseline Characteristics

Demographics and baseline characteristic data will be summarized for the safety population. Demographics data such as age (year), sex, ethnicity, race, weight (kg), height (cm) and BMI (kg/m^2) will be summarized as reported in the eCRF. In addition, the following derived characteristics will also be summarized as categorical data:

- Age (≤ 40 , > 40 to ≤ 60 , > 60 years old)
- Body Mass Index (< 25 , ≥ 25 to < 35 , ≥ 35 kg/m^2)

Medical history will be summarized for the medical history term. The primary diagnosis will be tabulated for body system, site and previous surgery. Operative data will be summarized for type of surgery, location and side, surgical technique, general anesthetic, local regional anesthetic, blood loss, tourniquet use, intervention, and time from surgery to enrolment. Discharge data will also be tabulated for ambulatory support use on discharge, primary ambulatory support and places the subject was discharged to.

5.6 Handling of Missing and Uninterpretable Data

Missing data will not be imputed, and the data will be analyzed as they were entered in the study database.

5.7 Determination of Sample Size

This study is precision-based, as a result, the sample size is not based on statistical power calculations. It is reasonable to assume a success rate of 95% for the MINITAC[◇] Ti 2.0 Suture Anchor in this study. With a further assumption of a $\pm 10\%$ precision in order to obtain a 95% CI of 85% to 100%, enrolling 30 subjects into the study will provide 55.4% probability. Across all investigational sites therefore, a minimum of 30 subjects (minimum of 10 subjects per site) up to a maximum of 50 subjects overall (98.8% probability) across all sites will be enrolled into this study.

5.8 Changes in the Conduct of the Planned Analysis

The following are changes from the protocol in the conduct of the planned analyses:

- In the protocol section 10.1, it is mentioned that generally all significance tests will be two-sided, performed at the 5% significance level, and resulting p-values will be quoted. However, for this study, given the small convenience study sample, the nature of non-intervention, as well as the absence of a priori statistical hypotheses, no formal hypothesis tests of statistical significance are planned, and as such, no p-values will be calculated. Relatedly, since statistical intervals are based on the same statistical assumptions as p values, no 95% confidence intervals will be estimated;
- The study will not employ separate safety and per protocol analysis sets. Instead, only one analysis set, the FAS as defined above, will be employed for all analyses;
- Kaplan-Meier estimation will not be used to estimate the event rate of postoperative device failure and/or device-related re-intervention at both 6 and 12-months. Instead incidence rates crude and model estimated incidence rates will be calculated;
- An analysis of the primary endpoint is included here +/- 3 months (3-9 month window) as per standard of care.

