#### **8.3.3 Subject Attrition**

Subject attrition due to reduction in sample size required for precision analysis has been accounted in the sample size calculation so that the estimate of the Confidence Interval (CI) to be obtained will still be valid through the most efficient use of available subjects.

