#### **8.3.4 Pre-specification of Statistical Analysis**

The primary outcome measure has been pre-specified as well as the type of statistical analysis to be performed to evaluate clinical success so as to minimize reporting bias. The exploratory data analysis planned for the study which include construction of confidence intervals for the outcome

Study Protocol—Device	
Safety and Performance of MINITAC® Ti 2.0 Suture Anchor in Extremities	Number: MINI.PMCF.2018.11
	Version: 3.0, 20Aug19
	Page: Page 24 of 56

summaries and a pre-defined range in which the 95% CI for the primary outcome are expected to fall within are designed to maximize the validity of the study results.

More detailed specifications will be incorporated in the Statistical Analysis Plan (SAP) so as minimize any threats to external validity in order to yield clinically relevant estimates of effects and precision.

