## 10.4 EFFICACY ANALYSIS

### 10.4.1 Analysis of Primary Endpoint

Clinical success rate at 6 months will be summarized using frequency (N) and percentage (%). A 95% exact CI for a single proportion will be presented for clinical success at 6 months using the Clopper-Pearson method (1934) (4). This analysis will be carried out using the PP population as the primary analysis population with the SAF population used for sensitivity analysis.

Study Protocol—Device	
Safety and Performance of MINITAC® Ti 2.0 Suture Anchor in Extremities	Number: MINI.PMCF.2018.11
	Version: 3.0, 20Aug19
	Page: Page 29 of 56

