#### 10.4.2 Analysis of Secondary Endpoint

Clinical success rate at 12 months will be summarized using frequency (N) and percentage (%). The same type of analysis described for the primary endpoint will be carried out on this secondary endpoint. This analysis will use the PP population as the primary analysis population and the SAF population for sensitivity analysis.

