5.2 General Presentation Considerations

As this study is of a descriptive nature, the analysis results will be reported using descriptive statistics.

Continuous data will be summarized in terms of the mean, standard deviation (SD), median, minimum, maximum and number of observations, unless otherwise stated. Continuous data that are expected to be skewed will be presented in terms of the maximum, upper quartile, median, lower quartile, minimum and number of observations. The minimum and maximum will be reported to the same number of decimal places as the raw data recorded in the database. The mean, median, lower quartile and upper quartile will be reported to one more decimal place than the raw data recorded in the database. The SD will be reported to two more decimal places than the raw data recorded in the database. In general, the maximum number of decimal places reported shall be four for any summary statistic.

Categorical data will be summarized in terms of the number of subjects providing data at the relevant time point (n), frequency counts and percentages. Percentages will be presented to one decimal place. Percentages will not be presented for zero counts. Percentages will be calculated using n as the denominator.

Given the small, convenience study sample, as well as the absence of *a priori* statistical hypotheses, no formal tests of statistical significance are planned, and as such, no p-values or statistical intervals will be calculated.

All report outputs will be produced using SAS[®] version 9.3 or a later version in a secure and validated environment. All report outputs will be provided to the Sponsor as individual .rtf files and as a consolidated .pdf document.

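### The SAP cancels the exact 95% confidence interval for clinical success while still justifying 30 to 50 subjects by the width of that interval

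*SAP*

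**What the plan says.** Protocol 10.4.1 commits to an interval for the primary endpoint: "A 95% exact CI for a single proportion will be presented for clinical success at 6 months using the Clopper-Pearson method". Protocol 10.4.2 extends it to 12 months: "The same type of analysis described for the primary endpoint will be carried out on this secondary endpoint". Two of the protocol's validity safeguards lean on it. Section 8.3.3 says attrition has been allowed for so that "the estimate of the Confidence Interval (CI) to be obtained will still be valid", and section 8.3.4 refers to "a pre-defined range in which the 95% CI for the primary outcome are expected to fall within".

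The SAP removes it. Section 5.2 states that "no p-values or statistical intervals will be calculated", and section 5.8 that "since statistical intervals are based on the same statistical assumptions as p values, no 95% confidence intervals will be estimated". The reasons given are the small convenience sample, the non-interventional design and the absence of a prior hypothesis. Sections 5.3.2 and 5.3.3 accordingly plan only a frequency and a percentage for clinical success.

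The sample size section was left as it stood in the protocol. SAP 5.7 reads "This study is precision-based, as a result, the sample size is not based on statistical power calculations". It assumes 95% success and a precision of ±10 points for a 95% interval, and then says "enrolling 30 subjects into the study will provide 55.4% probability", with 98.8% at 50 subjects.

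**The concern.** One section of the SAP justifies the number of subjects by the width of a confidence interval, and two others forbid calculating that interval. If the quoted probabilities really describe it, the only quantitative justification for the sample size refers to something the study will never report. The primary and secondary endpoints would then carry no planned statement of uncertainty for the success proportion, in a study of 30 to 50 subjects whose declared aim is precision.

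The stated reasons also need to be tested. An interval for a proportion needs no null hypothesis. The convenience-sample description sits badly with protocol 7.4 and 8.3.1, which prescribe consecutive screening and enrolment by surgery date to limit selection bias. A small sample is where an interval tells the reader most.

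**Working it through.** **Inputs.** True success rate 95%, precision ±10 points, N = 30 and N = 50 (SAP 5.7, protocol 11). Two-sided 95% intervals (protocol 10.1). Clopper-Pearson method (protocol 10.4.1).

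**Formulas.** For x successes in n subjects, the lower limit L is the 2.5% quantile of Beta(x, n−x+1) and the upper limit U is the 97.5% quantile of Beta(x+1, n−x). At x = n, U = 1. The half-width is h = (U−L)/2. The probability of meeting the target is the sum of C(n,x)·0.95^x·0.05^(n−x) over all x with h ≤ 0.10.

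**Step 1: reproduce the plan's figures.**

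- N = 30: h is 10.6 points at 28/30 and 8.6 points at 29/30, so at least 29 successes are needed. P = 30·0.95^29·0.05 + 0.95^30 = 0.3389 + 0.2146 = 0.5535, against the stated 55.4%.
- N = 50: h is 10.5 points at 43/50 and 9.9 points at 44/50, so at least 44 successes are needed. Summing x = 44 to 50: 0.0260 + 0.0658 + 0.1360 + 0.2199 + 0.2611 + 0.2025 + 0.0769 = 0.9882, against the stated 98.8%.

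**Step 2: try other readings.**

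| Criterion at a true rate of 95% | N = 30 | N = 50 |
|---|---|---|
| Stated in SAP 5.7 | 55.4% | 98.8% |
| Clopper-Pearson half-width ≤ 10 points | 55.35% | 98.82% |
| Clopper-Pearson lower limit ≥ 85% | 21.5% | 54.1% |
| Wald lower limit ≥ 85% | 55.4% | 76.0% |
| Wald half-width ≤ 10 points | 81.2% | 99.7% |
| Wilson half-width ≤ 10 points | 81.2% | 99.7% |

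Of these, only the exact half-width gives both figures. The SAP describes the target interval as 85% to 100%, but the probability that the exact interval lies wholly in that range is the third row. It needs 30/30 (0.2146) or at least 48/50 (0.2611 + 0.2025 + 0.0769 = 0.5405).

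**Step 3: what a bare percentage hides.**

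| Result | Percentage | Clopper-Pearson 95% interval | Half-width (points) | ±10 target |
|---|---|---|---|---|
| 28/30 | 93.3% | 77.9–99.2% | 10.6 | missed |
| 29/30 | 96.7% | 82.8–99.9% | 8.6 | met |
| 43/50 | 86.0% | 73.3–94.2% | 10.5 | missed |
| 44/50 | 88.0% | 75.7–95.5% | 9.9 | met |
| 47/50 | 94.0% | 83.5–98.7% | 7.6 | met |

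None of these five intervals excludes a true rate below 85%, including the three that meet the target.

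**Step 4: fewer evaluable subjects.** SAP 5.2 bases percentages on subjects with data, and SAP 5.6 imputes nothing, so the denominator may be below the number enrolled. The documents give no expected number. Assuming 25 to 29 evaluable out of 30, the probability of meeting the target is:

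| Evaluable n | 25 | 26 | 27 | 28 | 29 |
|---|---|---|---|---|---|
| Probability | 27.7% | 62.4% | 60.6% | 58.8% | 57.1% |

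The fall at 25 is a discreteness effect: 24/25 has a half-width of 10.13 points and just misses. The precision actually achieved therefore has to be read from the realised interval and cannot be inferred from the enrolment total.

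**The case against.** The strongest reply is that this is a disclosed reporting choice in a descriptive study. Protocol 10 provides for the SAP to record changes, and SAP 5.8 does so. No decision rule depends on the interval, SAP 1 says no regulatory submission is planned, and anyone can compute an exact interval from the count and denominator. The protocol synopsis also says the sample was set on feasibility, so SAP 5.7 could be read as a record of past planning. Finally, some statisticians decline intervals for non-random samples, and consecutive enrolment at up to three sites is not random sampling.

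Part of this stands. The change is not hidden, no data are lost and no estimate is biased. Feasibility is a second basis for the sample size, so the interval is its only quantitative justification but not its only basis.

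The rest does not answer the point. For this change SAP 5.8 refers only to protocol 10.1. It does not address 10.4.1, 10.4.2, 8.3.3 or 8.3.4, and it leaves SAP 5.7 in the present tense as a precision argument. The synopsis itself quotes the same interval probabilities beside the feasibility statement. An objection in principle to inference from this sample would apply equally to the model-estimated Poisson rates that SAP 5.3.2 and 5.3.3 retain.

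One further caution is fair. SAP 5.3.2 also requires no inflammation, no device-related adverse events and no device deficiencies, which the endpoint definition in protocol 8.2.1 does not list. The 95% planning rate may therefore not suit the endpoint as analysed. That makes reporting the realised interval more useful, not less.

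**Conclusion.** The concern holds and should be settled before the SAP is finalised. The SAP's 55.4% and 98.8% are the probabilities that a Clopper-Pearson 95% interval has a half-width of at most 10 points (recomputed as 55.35% and 98.82%), and the SAP forbids that interval. The consequence is a pre-specified statistic left unreported for both the primary and the secondary endpoint, and a sample-size section at odds with the analysis sections.

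The probabilities assume independent subjects, a true success rate of 95% and every enrolled subject evaluable. The intervals in Step 3 do not depend on the assumed 95% rate.

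**What to change.** - **SAP 5.2 and 5.8:** keep the statement that no p-values will be calculated, and delete the bar on intervals.
- **SAP 5.3.2 and 5.3.3:** report the two-sided 95% Clopper-Pearson interval for clinical success at 6 and 12 months in the full analysis set, the only set SAP 5.8 leaves. Give the count and denominator, and set the half-width beside the ±10-point planning target.
- **SAP 5.7:** state that 55.4% and 98.8% are the probabilities that the half-width is at most 10 points when the true rate is 95%. Do not let 85% to 100% be read as a pass/fail range, because the whole interval lies inside it with probability only 21.5% at 30 subjects and 54.1% at 50.
- Intervals for subgroups and incidence rates are optional.

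The cost is wording in five SAP sections and one option in the SAS frequency procedure. It needs no new data and no change to enrolment.
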